5.3.4 Endocrine Events

Thyroid disorders, adrenal insufficiency, diabetes mellitus, and pituitary disorders have been associated with the administration of atezolizumab. Management guidelines for endocrine events are provided in **Table 4**.

Patients with unexplained symptoms, such as headache, fatigue, myalgias, impotence, constipation or mental status changes, should be investigated for the presence of thyroid, pituitary, or adrenal endocrinopathies. The patient should be referred to an endocrinologist if an endocrinopathy is suspected. Thyroid-stimulating hormone (TSH) and free triiodothyronine and thyroxine levels should be measured to determine whether thyroid abnormalities are present. Pituitary hormone levels and function tests (e.g., TSH, growth hormone, luteinizing hormone, follicle-stimulating hormone, testosterone, prolactin, adrenocorticotrophic hormone [ACTH] levels, and ACTH stimulation test) and magnetic resonance imaging (MRI) of the brain (with detailed pituitary sections) may help to differentiate primary pituitary insufficiency from primary adrenal insufficiency.

Table 4: Management Guidelines for Endocrine Events

Event	Management
Grade 1 hypothyroidism	
Continue atezolizumab.Initiate treatment with thyroid replacement hormone.Monitor TSH closely.
Grade 2 hypothyroidism	
Consider withholding atezolizumab.Initiate treatment with thyroid replacement hormone.Monitor TSH closely.Consider patient referral to endocrinologist.Resume atezolizumab when symptoms are controlled, and thyroid function is improving.
Grade 3 and 4 hypothyroidism	
Withhold atezolizumab.Initiate treatment with thyroid replacement hormone.Monitor TSH closely.Refer to an endocrinologist.Admit patient to the hospital for developing myxedema (bradycardia, hypothermia, and altered mental status).Resume atezolizumab when symptoms are controlled, and thyroid function is improving.Permanently discontinue atezolizumab. ^c

Grade 1 hyperthyroidism	
TSH ≥ 0.1 mU/L and < 0.5 mU/L:
 
 Continue atezolizumab. Monitor TSH every 4 weeks. Consider patient referral to endocrinologist. 
TSH < 0.1 mU/L:
 
 Follow guidelines for Grade 2 hyperthyroidism. Consider patient referral to endocrinologist.
Grade 2 hyperthyroidism	
 Consider withholding atezolizumab. Initiate treatment with anti-thyroid drug such as methimazole or carbimazole as needed. Consider patient referral to endocrinologist. Resume atezolizumab when symptoms are controlled, and thyroid function is improving.
Grade 3 and 4 hyperthyroidism	
 Withhold atezolizumab. Initiate treatment with anti-thyroid drugs such as methimazole or carbimazole as needed. Refer to an endocrinologist. Resume atezolizumab when symptoms are controlled, and thyroid function is improving. Permanently discontinue atezolizumab. ^c
Symptomatic adrenal insufficiency, Grade 2–4	
 Withhold atezolizumab for up to 12 weeks after event onset. ^a Refer patient to endocrinologist. Perform appropriate imaging. Initiate treatment with corticosteroids equivalent to 1–2 mg/kg/day IV methylprednisolone and convert to 1–2 mg/kg/day oral prednisone or equivalent upon improvement. If event resolves to Grade 1 or better and patient is stable on replacement therapy, resume atezolizumab. ^b If event does not resolve to Grade 1 or better or patient is not stable on replacement therapy while withholding atezolizumab, permanently discontinue atezolizumab. ^c

Hyperglycemia, Grade 1 or 2	
 Continue atezolizumab. Investigate for diabetes. If patient has Type 1 diabetes, treat as a Grade 3 event. If patient does not have Type 1 diabetes, treat as per institutional guidelines. Monitor for glucose control.
Hyperglycemia, Grade 3 or 4	
 Withhold atezolizumab. Initiate treatment with insulin. Evaluate for diabetic ketoacidosis and manage as per institutional guidelines. Monitor for glucose control. Resume atezolizumab when symptoms resolve, and glucose levels are stable.
Hypophysitis (pan-hypopituitarism), Grade 2 or 3	
 Withhold atezolizumab for up to 12 weeks after event onset.^a Refer patient to endocrinologist. Perform brain MRI (pituitary protocol). Initiate treatment with corticosteroids equivalent to 1–2 mg/kg/day IV methylprednisolone and convert to 1–2 mg/kg/day oral prednisone or equivalent upon improvement. Initiate hormone replacement if clinically indicated. If event resolves to Grade 1 or better, resume atezolizumab.^b If event does not resolve to Grade 1 or better while withholding atezolizumab, permanently discontinue atezolizumab.^c For recurrent hypophysitis, treat as a Grade 4 event.
Hypophysitis (pan-hypopituitarism), Grade 4	
 Permanently discontinue atezolizumab.^c Refer patient to endocrinologist. Perform brain MRI (pituitary protocol). Initiate treatment with corticosteroids equivalent to 1–2 mg/kg/day IV methylprednisolone and convert to 1–2 mg/kg/day oral prednisone or equivalent upon improvement. Initiate hormone replacement if clinically indicated.

MRI = magnetic resonance imaging; TSH = thyroid-stimulating hormone.

^a Atezolizumab may be withheld for a longer period of time (i.e., > 12 weeks after event onset) to allow for corticosteroids (if initiated) to be reduced to the equivalent of \leq 10 mg/day oral prednisone. The acceptable length of the extended period of time must be based on the

investigator's benefit-risk assessment and in alignment with the protocol requirements for the duration of treatment and documented by the investigator.

^b If corticosteroids have been initiated, they must be tapered over \geq 1 month to the equivalent of \leq 10 mg/day oral prednisone before atezolizumab can be resumed.

^c Resumption of atezolizumab may be considered in patients who are deriving benefit and have fully recovered from the immune-mediated event. The decision to re-challenge patients with atezolizumab should be based on the investigator's benefit-risk assessment and documented by the investigator.

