5.3 Atezolizumab Dose Management and Modifications

Toxicities associated or possibly associated with atezolizumab treatment should be managed according to standard medical practice. Additional tests, such as autoimmune serology or biopsies, should be used to evaluate for a possible immunogenic etiology.

Although most immune-mediated adverse events observed with immunomodulatory agents have been mild and self-limiting, such events should be recognized early and treated promptly to avoid potential major complications. Discontinuation of atezolizumab may not have an immediate therapeutic effect, and in severe cases, immune-mediated toxicities may require acute management with topical corticosteroids, systemic corticosteroids, or other immunosuppressive agents.

The investigator should consider the benefit versus risk balance a given patient may be experiencing prior to further administration of atezolizumab. In patients who have met the criteria for permanent discontinuation, resumption of atezolizumab may be considered if the patient is deriving benefit and has fully recovered from the immune-mediated event. Patients can be rechallenged with atezolizumab only after approval has been documented by the study investigator.

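### Table 4 says both to resume and to permanently stop atezolizumab after a Grade 3 or 4 thyroid event, and puts no condition on the stop

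*Combined protocol and SAP*

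**What the plan says.** Table 4 (section 5.3.4) covers endocrine events on atezolizumab. Both Grade 3 and 4 thyroid rows begin with withholding the drug, then give treatment and an endocrinology referral. The hypothyroidism row closes with "Resume atezolizumab when symptoms are controlled, and thyroid function is improving.Permanently discontinue atezolizumab", and the hyperthyroidism row with "thyroid function is improving. Permanently discontinue atezolizumab". Each discontinue bullet carries footnote c.

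Footnote c reads: "Resumption of atezolizumab may be considered in patients who are deriving benefit and have fully recovered from the immune-mediated event". It adds that the decision rests on a documented benefit-risk assessment by the investigator. The opening text of section 5.3 sets the same standard once a patient has been stopped for good: "resumption of atezolizumab may be considered if the patient is deriving benefit and has fully recovered from the immune-mediated event". It also requires documented approval from the study investigator before any rechallenge.

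Two other rows of Table 4 contain both a resume and a discontinue instruction. For adrenal insufficiency, Grade 2 to 4, the stop reads "If event does not resolve to Grade 1 or better or patient is not stable on replacement therapy while withholding atezolizumab, permanently discontinue atezolizumab". For hypophysitis, Grade 2 or 3, it reads "If event does not resolve to Grade 1 or better while withholding atezolizumab, permanently discontinue atezolizumab".

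**The concern.** A dose-management table should give one instruction for a given patient state. Here a conditional restart is followed by an unconditional permanent stop, with no grade, outcome or time that triggers the stop. Two investigators could handle similar patients differently and each be able to cite the table. One would re-expose a patient whom the table says to stop; the other would withdraw drug from a patient whom the table says may resume. What is at stake is safe and uniform atezolizumab dosing.

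**Working it through.** The point turns on wording and involves no statistical calculation. The check sets the provisions side by side.

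**1. How many rows are affected.** Table 4 has 3 hypothyroidism rows (Grade 1, 2, 3 and 4 together), 3 hyperthyroidism rows (same split), 1 adrenal insufficiency row, 2 hyperglycemia rows and 2 hypophysitis rows: 3 + 3 + 1 + 2 + 2 = 11. Those with both a resume and a discontinue instruction are:

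| Row | Condition on resuming | Condition on discontinuing |
|---|---|---|
| Hypothyroidism, Grade 3 and 4 | symptom control and improving thyroid function | none |
| Hyperthyroidism, Grade 3 and 4 | same | none |
| Adrenal insufficiency, Grade 2–4 | Grade 1 or better and stable on replacement | either of these not reached during the hold |
| Hypophysitis, Grade 2 or 3 | Grade 1 or better | not reached during the hold |

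So 2 of 11 rows, and 2 of these 4, lack a trigger.

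**2. Whether footnote c reconciles the two bullets.** The row's resume standard is symptom control plus improving function. Footnote c requires benefit plus full recovery, and then only permits resumption. Improving is less than fully recovered, and the resume bullet does not mention benefit. Three cases follow:

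- *Resume standard not met.* No drug is given under either bullet. They differ only on whether the hold is temporary or permanent.
- *Resume standard and footnote c both met.* The first bullet restarts the drug. The second leaves restart open, subject to the documented assessment and approval. The two are partly reconciled.
- *Resume standard met, footnote c not met* (not fully recovered, or not deriving benefit). The first bullet restarts the drug; the second keeps the patient off it. The instructions are opposite.

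**3. Whether another section settles it.** Section 5.2 lets the medical oncologist stop for toxicity or progression. Section 8.5 requires stopping when the investigator judges an immune-mediated event unacceptable. Neither names a thyroid trigger or says which bullet prevails.

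**4. Whether the rest of the table shows the intent.** It does not. Adrenal insufficiency and hypophysitis Grade 2 or 3 use discontinuation as a fallback when recovery fails. Hypophysitis also splits by grade, with Grade 4 going straight to discontinuation. Hyperglycemia Grade 3 or 4 has only a resume bullet, "Resume atezolizumab when symptoms resolve, and glucose levels are stable". For a controlled Grade 4 thyroid patient, the fallback pattern means resume and the grade split means stay off.

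**5. Reach into the primary analysis.** Section 3.1 makes radiation dose the escalated agent. Under section 8.2.1, a DLT is failure to complete radiation in time, Grade 4+ toxicity attributed to radiation, or a treatment-related death. The choice to resume or stop atezolizumab is not itself an input.

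**The case against.** The strongest reply is that the order of the bullets (withhold, treat, refer, resume when controlled, discontinue) matches the adrenal and hypophysitis Grade 2 or 3 rows. A clinician would then read the last bullet as the fallback, and the conflict disappears. Table 4 is also labelled as guidelines, section 5.3 calls for a benefit-risk judgment before further dosing, and both rows require endocrinology referral. This stands as mitigation, so it would go too far to say the rows cannot be followed. But the condition has to be supplied by the reader, and the grade split in the hypophysitis rows is an equally available model that gives a different answer at Grade 4.

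Loss of text in PDF conversion is possible but unlikely: both rows end with the same complete sentence and footnote mark.

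A reader might infer that any patient controlled on thyroid replacement is caught, because such a patient is not fully recovered. The documents do not support that. They never define full recovery, the adrenal row allows resumption when stable on replacement, and exclusions 20 and 35 admit patients with hypothyroidism on replacement.

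A reader might also infer that the MTD is compromised. That is not shown either. A treatment-related death counts as a DLT, and one after re-exposure is conceivable, but nothing in the documents links such an event to these rows or gives it a size. One-year survival and locoregional control are measured while atezolizumab is being given, so an indirect influence cannot be excluded, but it cannot be quantified.

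**Conclusion.** The inconsistency is real and minor. Both Grade 3 and 4 thyroid rows pair a conditional restart with an unconditional permanent stop. For a patient who meets the row's resume standard but not footnote c, the two bullets require opposite actions, and nothing else in the protocol decides between them.

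The size is two table rows. Because the protocol gives no thyroid event rate, the number of patients or doses affected is unknown. The conclusion assumes only that improving means something less than fully recovered, and that the published table matches the protocol in use. The consequence is confined to the safety and consistency of atezolizumab dosing, softened by investigator discretion and specialist referral.

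**What to change.** Put a condition on the last bullet of both rows. The version that adds least is: *permanently discontinue only if, during the hold, symptoms stay uncontrolled or thyroid function fails to improve (footnote c applies)*. This follows the fallback pattern of the adrenal row. It does not need that row's limit, "Withhold atezolizumab for up to 12 weeks after event onset", which neither thyroid row contains.

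If the sponsor intended a grade split as for hypophysitis, restrict the resume bullet to Grade 3 and state that Grade 4 means permanent discontinuation, subject to footnote c. The choice is clinical: the first version lets a controlled Grade 4 patient restart, and the second keeps that patient off unless footnote c is met. The same choice should apply to both rows.

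The cost is a short protocol amendment with IRB approval before implementation, as section 10.5.3 requires. Design, sample size and analysis do not change.

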5.3.5 Ocular Events

An ophthalmologist should evaluate visual complaints (e.g., uveitis, retinal events). Management guidelines for ocular events are provided in [Table 5](#).

Table 5 Management Guidelines for Ocular Events

Event	Management
Ocular event, Grade 1	
Continue atezolizumab.Patient referral to ophthalmologist is strongly recommended.Initiate treatment with topical corticosteroid eye drops and topical immunosuppressive therapy.If symptoms persist, treat as a grade 2 event.
Ocular event, Grade 2	
Withhold atezolizumab for up to 12 weeks after event onset.^aPatient referral to ophthalmologist is strongly recommended.Initiate treatment with topical corticosteroid eye drops and topical immunosuppressive therapy.If event resolves to grade 1 or better, resume atezolizumab.^bIf event does not resolve to grade 1 or better while withholding atezolizumab, permanently discontinue atezolizumab and contact study investigator.^c
Ocular event, Grade 3 or 4	
Permanently discontinue atezolizumab and contact study investigator.^cRefer patient to ophthalmologist.Initiate treatment with corticosteroids equivalent to 1–2 mg/kg/day oral prednisone.If event resolves to grade 1 or better, taper corticosteroids over one month.

^a Atezolizumab may be withheld for a longer period of time (i.e., 12 weeks after event onset) to allow for corticosteroids (if initiated) to be reduced to the equivalent of 10-mg/day oral prednisone. The acceptable length of the extended period of time must be on the investigator's benefit risk assessment and in alignment with the protocol requirements for the duration of treatment and documented by the investigator.

- b If corticosteroids have been initiated, they must be tapered over one month to the equivalent of 10-mg/day oral prednisone before atezolizumab can be resumed.
- c Resumption of atezolizumab may be considered in patients who are deriving benefit and have fully recovered from the immune-mediated event. The decision to re challenge patients with atezolizumab should be based on the investigator's benefit risk assessment and documented by the investigator.

5.3.6 Immune-Mediated Myocarditis

Immune-mediated myocarditis has been associated with the administration of atezolizumab. Immune-mediated myocarditis should be suspected in any patient presenting with signs or symptoms suggestive of myocarditis, including, but not limited to, laboratory (e.g., B-type natriuretic peptide) or cardiac imaging abnormalities, dyspnea, chest pain, palpitations, fatigue, decreased exercise tolerance, or syncope. Immune-mediated myocarditis needs to be distinguished from myocarditis resulting from infection (commonly viral, e.g., in a patient who reports a recent history of gastrointestinal illness), ischemic events, underlying arrhythmias, exacerbation of preexisting cardiac conditions, or progression of malignancy.

All patients with possible myocarditis should be urgently evaluated by performing cardiac enzyme assessment, an ECG, a chest X-ray, an echocardiogram, and a cardiac MRI as appropriate per institutional guidelines. A cardiologist should be consulted. An endomyocardial biopsy may be considered to enable a definitive diagnosis and appropriate treatment, if clinically indicated.

Patients with signs and symptoms of myocarditis, in the absence of an identified alternate etiology, should be treated according to the guidelines in [Table 6](#).

IMMUNE-MEDIATED PERICARDIAL DISORDERS

Immune-mediated pericarditis should be suspected in any patient presenting with chest pain and may be associated with immune-mediated myocarditis (see section on myocarditis above).

Immune-mediated pericardial effusion and cardiac tamponade should be suspected in any patient presenting with chest pain associated with dyspnea or hemodynamic instability.

Patients should be evaluated for other causes of pericardial disorders such as infection (commonly viral), cancer related (metastatic disease or chest radiotherapy), cardiac injury related (post myocardial infarction or iatrogenic), and autoimmune disorders, and should be managed accordingly.

All patients with suspected pericardial disorders should be urgently evaluated by performing an ECG, chest X-ray, transthoracic echocardiogram, and cardiac MRI as appropriate per institutional guidelines. A cardiologist should be consulted. Pericardiocentesis should be considered for diagnostic or therapeutic purposes, if clinically indicated.

Patients with signs and symptoms of pericarditis, pericardial effusion, or cardiac tamponade, in the absence of an identified alternate etiology, should be treated according to the guidelines in **Error! Reference source not found.** Withhold treatment with atezolizumab for Grade 1 pericarditis and conduct a detailed cardiac evaluation to determine the etiology and manage accordingly.

Table 6 Management Guidelines for Immune-Mediated Cardiac Events

Event	Management
Immune-mediated myocarditis, Grades 2–4	
Permanently discontinue atezolizumab.Refer patient to cardiologist.
Immune-mediated pericardial disorders, Grades 2–4	
Initiate treatment as per institutional guidelines and consider antiarrhythmic drugs, temporary pacemaker, ECMO, VAD, or pericardiocentesis as appropriate.Initiate treatment with corticosteroids equivalent to 1–2 mg/kg/day IV methylprednisolone and convert to 1–2 mg/kg/day oral prednisone or equivalent upon improvement.If event does not improve within 48 hours after initiating corticosteroids, consider adding an immunosuppressive agent.If event resolves to Grade 1 or better, taper corticosteroids over \geq 1 month.

ECMO = extracorporeal membrane oxygenation; VAD = ventricular assist device.

5.3.7 INFUSION-RELATED REACTIONS AND CYTOKINE-RELEASE SYNDROME

No premedication is indicated for the administration of Cycle 1 of atezolizumab. However, patients who experience an infusion-related reaction (IRR) or cytokine-release syndrome (CRS) with atezolizumab may receive premedication with antihistamines, antipyretic medications, and/or analgesics (e.g., acetaminophen) for subsequent infusions. Metamizole (dipyrone) is prohibited in treating atezolizumab-associated IRRs because of its potential for causing agranulocytosis.

IRRs are known to occur with the administration of monoclonal antibodies and have been reported with atezolizumab. These reactions, which are thought to be due to release of cytokines and/or other chemical mediators, occur within 24 hours of atezolizumab administration and are generally mild to moderate in severity.

CRS is defined as a supraphysiologic response following administration of any immune therapy that results in activation or engagement of endogenous or infused T cells and/or other immune effector cells. Symptoms can be progressive, always include fever at the onset, and may include hypotension, capillary leak (hypoxia), and end-organ dysfunction (Lee et al. 2019). CRS has been well documented with chimeric antigen receptor T-cell therapies and bispecific T-cell engager antibody therapies but has also been reported with immunotherapies that target PD-1 or PD-L1 (Rotz et al. 2017; Adashek and Feldman 2019), including atezolizumab.

There may be significant overlap in signs and symptoms of IRRs and CRS, and in recognition of the challenges in clinically distinguishing between the two, consolidated guidelines for the medical management of IRRs and CRS are provided in [Error! Reference source not found.](#)

Severe SARS-CoV-2 infection appears to be associated with a CRS involving the inflammatory cytokines interleukin (IL)-6, IL-10, IL-2, and IFN- γ (Merad and Martin 2020). If a patient develops suspected CRS during the study, a differential diagnosis should include SARS-CoV-2 infection, which should be confirmed or refuted through assessment of exposure history, appropriate laboratory testing, and clinical or radiologic evaluations per investigator's judgment. If a diagnosis of SARS-CoV-2 infection is confirmed, the disease should be managed as per local or institutional guidelines.

Table 7 Management Guidelines for Infusion-Related Reactions and Cytokine-Release Syndrome

Event	Management
Grade 1 ^a Fever ^b with or without constitutional symptoms	
 • Immediately interrupt infusion. • Upon symptom resolution, wait 30 minutes and then restart infusion at half the rate being given at the time of event onset. • If the infusion is tolerated at the reduced rate for 30 minutes, the infusion rate may be increased to the original rate. • If symptoms recur, discontinue infusion of this dose. • Administer symptomatic treatment,^c including maintenance of IV fluids for hydration. • In case of rapid decline or prolonged CRS (> 2 days) or in patients with significant symptoms and/or comorbidities, consider managing as per Grade 2. • For subsequent infusions, consider administration of oral premedication with antihistamines, anti-pyretics, and/or analgesics, and monitor closely for IRRs and/or CRS.


Grade 2^a
 
Fever^b with hypotension not requiring vasopressors and/or
 
Hypoxia requiring low-flow oxygen^d by nasal cannula or blow-by
	
 ● Immediately interrupt atezolizumab infusion. ● Upon symptom resolution, wait for 30 minutes and then restart infusion at half the rate being given at the time of event onset. ● If symptoms recur, discontinue infusion of this dose. ● Administer symptomatic treatment.^c ● For hypotension, administer IV fluid bolus as needed. ● Monitor cardiopulmonary and other organ function closely (in the ICU, if appropriate). Administer IV fluids as clinically indicated and manage constitutional symptoms and organ toxicities as per institutional practice. ● Rule out other inflammatory conditions that can mimic CRS (e.g., sepsis). If no improvement within 24 hours, initiate workup and assess for signs and symptoms of HLH or MAS. ● Consider IV corticosteroids (e.g., methylprednisolone 2 mg/kg/day or dexamethasone 10 mg every 6 hours). ● Consider anti-cytokine therapy.^e ● Consider hospitalization until complete resolution of symptoms. If no improvement within 24 hours, manage as per Grade 3, that is, hospitalize patient (monitoring in the ICU is recommended), permanently discontinue atezolizumab. ● If symptoms resolve to Grade 1 or better for 3 consecutive days, the next dose of atezolizumab may be administered. For subsequent infusions, consider administration of oral premedication with antihistamines, anti-pyretics, and/or analgesics and monitor closely for IRRs and/or CRS. ● If symptoms do not resolve to Grade 1 or better for 3 consecutive days, contact the sponsor-investigator.
---	---


Grade 3^a Fever^b with hypotension requiring a vasopressor (with or without vasopressin) and/or Hypoxia requiring high-flow oxygen^d by nasal cannula, face mask, non-rebreather mask, or venturi mask
	
 • Permanently discontinue atezolizumab.^f • Administer symptomatic treatment.^c • For hypotension, administer IV fluid bolus and vasopressor as needed. • Monitor cardiopulmonary and other organ function closely; monitoring in the ICU is recommended. Administer IV fluids as clinically indicated and manage constitutional symptoms and organ toxicities as per institutional practice. • Rule out other inflammatory conditions that can mimic CRS (e.g., sepsis). If no improvement within 24 hours, initiate workup and assess for signs and symptoms of HLH or MAS. • Administer IV corticosteroids (e.g., methylprednisolone 2 mg/kg/day or dexamethasone 10 mg every 6 hours). • Consider anti-cytokine therapy.^e • Hospitalize patient until complete resolution of symptoms. If no improvement within 24 hours, manage as per Grade 4, that is, admit patient to ICU and initiate hemodynamic monitoring, mechanical ventilation, and/or IV fluids and vasopressors as needed; for patients who are refractory to anti-cytokine therapy, experimental treatments may be considered at the discretion of the investigator.

Grade 4^a Fever^b with hypotension requiring multiple vasopressors (excluding vasopressin) and/or Hypoxia requiring oxygen by positive pressure (e.g., CPAP, BiPAP, intubation and mechanical ventilation)
	
 • Permanently discontinue atezolizumab.^f • Administer symptomatic treatment.^c • Admit patient to ICU and initiate hemodynamic monitoring, mechanical ventilation, and/or IV fluids and vasopressors as needed. Monitor other organ function closely. Manage constitutional symptoms and organ toxicities as per institutional practice. • Rule out other inflammatory conditions that can mimic CRS (e.g., sepsis). If no improvement within 24 hours, initiate workup and assess for signs and symptoms of HLH or MAS. • Administer IV corticosteroids (e.g., methylprednisolone 2 mg/kg/day or dexamethasone 10 mg every 6 hours). • Consider anti-cytokine therapy.^e For patients who are refractory to anti-cytokine therapy, experimental treatments^g may be considered at the discretion of the investigator. • Hospitalize patient until complete resolution of symptoms.

ASTCT= American Society for Transplantation and Cellular Therapy; BiPAP= bi-level positive airway pressure; CAR= chimeric antigen receptor; CPAP= continuous positive airway pressure; CRS= cytokine-release syndrome; HLH= hemophagocytic lymphohistiocytosis; IRR = infusion-related reaction; MAS= macrophage activation syndrome.

Note: The management guidelines have been adapted from NCCN guidelines for management of CAR T-cell-related toxicities (Version 2.2019).

- a. Grading system for management guidelines is based on ASTCT consensus grading for CRS. NCI CTCAE (version as specified in the protocol) should be used when reporting severity of IRRs, CRS, or organ toxicities associated with CRS on the Adverse Event eCRF. Organ toxicities associated with CRS should not influence overall CRS grading.
- b. Fever is defined as temperature $\geq 38^{\circ}\text{C}$ not attributable to any other cause. In patients who develop CRS and then receive anti-pyretic, anti-cytokine, or corticosteroid therapy, fever is no longer required when subsequently determining event severity (grade). In this case, the grade is driven by the presence of hypotension and/or hypoxia.
- c. Symptomatic treatment may include oral or IV antihistamines, anti-pyretics, analgesics, bronchodilators, and/or oxygen. For bronchospasm, urticaria, or dyspnea, additional treatment may be administered as per institutional practice.
- d. Low flow is defined as oxygen delivered at $\leq 6 \text{ L/min}$, and high flow is defined as oxygen delivered at $> 6 \text{ L/min}$.
- e. There are case reports where anti-cytokine therapy has been used for treatment of CRS with immune checkpoint inhibitors (Rotz et al. 2017; Adashek and Feldman 2019), but data are limited, and the role of such treatment in the setting of antibody-associated CRS has not been established.
- f. Resumption of atezolizumab may be considered in patients who are deriving benefit and have fully recovered from the immune-related event. Patients can be re-challenged with atezolizumab according to institutional guidelines and the above table. For subsequent infusions, administer oral premedication with antihistamines, anti-pyretics, and/or analgesics, and monitor closely for IRRs and/or CRS. Premedication with corticosteroids and extending the infusion time may also be considered after considering the benefit-risk ratio.
- g. Refer to Riegl et al. [61] for information on experimental treatments for CRS.

